3.3.2 KNOWN POTENTIAL BENEFITS

This study has not been designed to benefit the individual participants.

3.3.3 Assessment of Potential Risks and Benefits

The risks and benefits presented above are no more serious than for other clinical trials in this population. Based on the need for complementary and alternative treatments for MDD, the potential risks are worth the potential benefits. Furthermore, this is an open-label study that does not require considerations about the risks associated with a placebo group. We also note that the FDA has recently confirmed a non-significant risk (NSR) status for a very similar tACS trial in MDD.

4. OBJECTIVES AND OUTCOME MEASURES

OBJECTIVES	ENDPOINTS	JUSTIFICATION FOR ENDPOINTS
Primary		
To determine the effect of CLtACS on depression symptom severity	Change in HDRS-17 between two-week follow-up (FU2) and Day 1 (D1)	The HDRS-17 is the standard clinician-administered instrument to measure change in symptom severity in people with MDD
Secondary		
To determine the effect of CLtACS on depression symptom severity	Change in HDRS-17 between D5 and Baseline/ D1	The HDRS-17 is the standard clinician-administered instrument to measure change in symptom severity in people with MDD.
To determine the remission and response rate of CLtACS Response is defined as >= 50% reduction rate in HDRS-17 score relative to D1 Remission is defined as	Number of response/remission rates at D5 and FU2	Remission and response rates provide additional insights into the efficacy of a treatment.

OBJECTIVES	ENDPOINTS	JUSTIFICATION FOR ENDPOINTS
To determine time-course of symptom change	Change in Quick Inventory of Depressive Symptomatology (QIDS) at D5, FU1, FU2	Battery of self-report measures of mood and related constructs at the 7-day follow up (digitally
	Change in Altman Self-Rating Mania Scale (ASRM) at D5, FU1, FU2	delivered) provide additional insights into the symptom changes in between the
	Change in Snaith-Hamilton Pleasure Scale (SHAPS) at D5, FU1, FU2	clinician administered assessment on Day 5 and at FU2.
	Change in Depression Anxiety and Stress Scale (DASS-42) at D5, FU1, FU2	
	Change in State-Train Anxiety Inventory (STAI) at D5, FU1, FU2	
	Change in Quality of Life Enjoyment and Satisfaction Questionnaire, short form (Q-LES-Q-SE) at D5_EU1_EU2	
	Change in Clinical Global Impression Scale (CGI) at D5, FU2	
Exploratory		
Feasibility	Fraction of participants who complete the 5-day course of stimulation	Since the primary outcome is determined from the subgroup of people who have completed stimulation, examining the fraction of people who complete the stimulation paradigm is important to minimize bias in case of people discontinuing study participation due to lack of perceived efficacy or symptoms worsening.
To determine the effect of CLtACS on endogenous EEG alpha oscillations	Change in HD-EEG alpha oscillation power at D1 pre-stimulation, D1 post-stimulation, and FU2	The inclusion of EEG endpoints provides insights into the network-level mechanisms underlying the treatment effects.

OBJECTIVES	ENDPOINTS	JUSTIFICATION FOR ENDPOINTS				
To determine time-course of symptom change	Change in Quick Inventory of Depressive Symptomatology (QUIDS) at FU3, FU4, FU5, FU6, FU7 Change in Altman Self-Rating Mania Scale (ASRM) at FU3,	Battery of self-report measures of mood and related constructs provide additional insights into the symptom changes in between the clinician administered assessment on				
	FU4, FU5, FU6, and FU7 Change in Depression Anxiety and Stress Scale (DASS-42) at FU3, FU4, FU5, FU6, and FU7	D5, FU2, and FU4. Time-scale of symptom change				
	Change in State-Train Anxiety Inventory (STAI) at FU3, FU4, FU5, FU6, and FU7	for the design of future, large-scale treatment studies.				
	Change in Snaith-Hamilton Pleasure Scale (SHAPS) FU3, FU4, FU5, FU6, and FU7					
	Change Quality of Life Enjoyment and Satisfaction Questionnaire, short form (Q-LES-Q-SF) at FU3, FU4, FU5,					
	FU6, and FU7					
To determine the effect of CLtACS on depression symptom severity	Change in HDRS-17 between six week follow up (FU4) and D1	The HDRS-17 is the standard clinician-administered instrument to measure change in symptom severity in people with MDD.				

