8. STUDY INTERVENTION DISCONTINUATION AND PARTICIPANT DISCONTINUATION/WITHDRAWAL

8.1 DISCONTINUATION OF STUDY INTERVENTION

Discontinuation from the week of stimulation does not mean discontinuation from the study, and remaining study procedures should be completed as indicated by the study protocol. If a clinically

significant finding is identified (including, but not limited to changes from baseline) after enrollment, the investigator or qualified designee will determine if any change in participant management is needed.

The study intervention (i.e., the 5 consecutive days of stimulation) will be discontinued for the following reasons:

- A participant develops significantly increased suicidal risk, as determined by an acute assessment by [name] or [name].
- A participant has an ASRM score greater than or equal to 6.
- The participant misses a single day of stimulation and is unable to make it up at the end of the stimulation week.
- Any clinical adverse event (AE), laboratory abnormality, intercurrent illness or other medical condition, or situation occurs such that continued participation in the study would not be in the best interest of the participant.
- The participant meets any exclusion criteria (either newly developed or not previously recognized).

If the participant withdraws from the intervention, the participant will be contacted and invited for the FU1 survey questionnaires and for the FU2 follow-up assessment including all respective questionnaires. These assessments are not intended as a clinical follow-up with the participants but serve research purposes only.

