8.2 PARTICIPANT DISCONTINUATION/WITHDRAWAL FROM THE STUDY

Participants are free to withdraw from participation in the study at any time and without having to give a reason. If the participant is willing to give a reason for discontinuation or withdrawal from the study, it will be recorded with the participant files. Participants who sign the informed consent form and do not receive stimulation will be replaced. Participants who sign the informed consent form and receive only part of the study intervention OR withdraw or are withdrawn or discontinue from the study prior to the 2-week follow-up will not be replaced. The maximum number of participants consented will be 35.

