10.3 POPULATIONS FOR ANALYSES

Every effort will be made to ensure all enrolled participants complete all study sessions as described in this protocol.

As previously stated in **Section 7 Study Intervention Discontinuation and Participant Discontinuation/Withdrawal**, enrolled participants who do not complete the full intervention will be replaced. Therefore, with this population for analysis plan, we anticipate having data from 35 participants that are eligible for analysis.

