10.4.2 ANALYSIS OF THE PRIMARY EFFICACY ENDPOINT (DEPRESSION SEVERITY)

We will perform a paired t-test to establish the statistical significance of the change in depression symptom severity (two-sided, alpha = 0.05). Additional, strictly exploratory analyses will take into account baseline scores as covariates (e.g., degree of treatment resistance measured by the Maudsley scale).

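### The only stated population for the primary HDRS-17 analysis is stimulation completers, although people who stop are invited to FU2; and section 10.3 conflicts with 8.2 on replacement and with 10.2 on the number analysed

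*Combined protocol and SAP*

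**What the plan says.** **Who is analysed.** The primary endpoint is the HDRS-17 change between D1 and FU2. Neither its row in section 4 nor the hypotheses in 10.1 name a population. Section 10.4.2 says only "We will perform a paired t-test to establish the statistical significance of the change in depression symptom severity". The one explicit statement is in the Feasibility row of section 4, which opens its justification with "Since the primary outcome is determined from the subgroup of people who have completed stimulation". The same cell gives lack of perceived efficacy and worsening as reasons why people might leave, and offers the completion fraction as protection against bias.

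**What is collected after stopping.** Section 8.1 says "Discontinuation from the week of stimulation does not mean discontinuation from the study", and that after withdrawal from the intervention "the participant will be contacted and invited for the FU1 survey questionnaires and for the FU2 follow-up assessment including all respective questionnaires".

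**Replacement and numbers.** Section 10.3, headed as the populations section, says "enrolled participants who do not complete the full intervention will be replaced" and "we anticipate having data from 35 participants that are eligible for analysis". Section 8.2 replaces only people who consent and are never stimulated. Those who receive part of the intervention, or who "discontinue from the study prior to the 2-week follow-up will not be replaced". It adds: "The maximum number of participants consented will be 35". Section 10.2 plans to consent about 35 in order to have 28 complete datasets, on 80% completion of all sessions.

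**Missing data.** Section 8.3 says the analysis plan allows for missing data. Section 10 contains no method for it.

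**The concern.** People who stop a five-day treatment may stop because they are not improving. If their FU2 scores exist but are not used, the mean change is computed in a selected group, and a single-arm study has no comparison group that would show the selection. Publishing the completion fraction tells the reader that selection occurred; it does not change the HDRS-17 estimate. That estimate is the main product of the pilot, so a loss that can be avoided with data the protocol already offers to collect is worth avoiding. The denominators for response and remission in 10.4.3 are left open in the same way.

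The conflict between 10.3 and the two other sections is a separate matter. It leaves unclear who is replaced, how many people the analysis is expected to contain, and therefore what precision was planned.

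**Working it through.** **1. The plan's own figures.** For a paired t-test at two-sided 0.05, power comes from the noncentral t distribution with n − 1 degrees of freedom and noncentrality dz × √n.
- dz = 1.58, n = 8: power 0.967 (n = 7 gives 0.933), so N = 8 for 95% power is right.
- dz = 1, n = 10: power 0.803, as stated.
- dz = 0.55, n = 28: power 0.801, as stated.
- 28 / 0.80 = 35 consents, as stated. In the earlier trial 26/32 = 81%, which fits the 80%.

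The arithmetic of 10.2 is sound.

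**2. The 35 in 10.3.** With consent capped at 35, 35 analysable participants means no loss at all.
- At the earlier trial's stimulation completion (30 of 32): 35 × 32/30 = 37.3, so 38 consents.
- At 80% completion of all sessions: 35 / 0.80 = 43.75, so 44 consents.

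Both exceed the cap. The dz detectable at 80% power is 0.549 with 28 and 0.487 with 35.

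**3. Replacement.** For someone who starts stimulation and does not finish, 10.3 says replaced and 8.2 says not replaced. Section 10.3 presents its rule as a restatement of an earlier section, which it numbers as 7. The replacement rule now stands in section 8, and it says the opposite.

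**4. Size of the completer restriction.** The expected number of stoppers is 35 × 2/32 = 2.2, so about 2. Take improvement as standard normal in 35 people, and let the k who stop be the lowest k on a variable that correlates r with improvement. The completer mean then shifts by

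shift = r × (sum of the k lowest expected normal order statistics of 35, sign reversed) / (35 − k).

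The three lowest are −2.107, −1.690 and −1.448. For k = 2: (2.107 + 1.690) / 33 = 0.115.

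| Stoppers | r = 0 | r = 0.3 | r = 0.5 |
|---|---|---|---|
| 1 | 0 | 0.019 SD | 0.031 SD |
| 2 | 0 | 0.035 SD | 0.058 SD |
| 3 | 0 | 0.049 SD | 0.082 SD |

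For 2 stoppers this is 2.2% / 3.6% of dz 1.58 and 6.3% / 10.5% of dz 0.55. The documents give no r; these values are assumptions. The 32 in the earlier trial are described as enrolled and may not all have been treated, so 2 may be too many.

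A cruder check does not use r. If both stoppers had no change at all, the all-treated mean would be 33/35 = 94% of the completer mean.

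**5. Significance.** At dz 1.58 power exceeds 99.9% with 28, 33 or 35 people. The choice of set affects the estimate, not whether the test succeeds at the expected effect.

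**The case against.** The restriction is an aside in the justification of an exploratory endpoint. The primary endpoint row, the hypotheses and 10.4.2 do not carry it, and 8.1 makes a point of collecting FU2 data from people who stop. A reader might infer that the plan formally prescribes a completer analysis. The documents do not go that far. What stands is that nothing else names a set, nothing overrides the clause, and the replacement of non-completers in 10.3 leans the same way.

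The effect in people who receive the full course is also a recognisable target for an open-label pilot, and the protocol pairs it with a completion fraction over everyone stimulated. That is a reason to keep the completer result as supportive. It is not a reason to set aside FU2 scores already in hand when the protocol itself names the bias.

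The bias is small, and some reasons for stopping, such as a missed day that cannot be made up, need not relate to outcome. Both points are accepted. Some stoppers may also have no FU2 score: sections 3.3.1, 6.5, 9.2.1 and 9.2.2 describe ending or withdrawing participation in circumstances where 8.1 would continue follow-up. The gain from including stoppers may therefore be partial.

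Finally, the text in 10.3 may be left over from another version and 8.2 may be the operative rule. That would make the correction editorial, but it is still needed, because 10.3 is where an analyst will look.

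**Conclusion.** The point holds at moderate weight and should be fixed before analysis. On the text alone, the primary population is stated only in passing, as stimulation completers, and section 10 neither confirms nor replaces that. The likely overstatement is about 0.035 to 0.058 SD for 2 stoppers, if r is 0.3 to 0.5; it is zero if stopping is unrelated to outcome. The inconsistency in 10.3 needs no assumption: its replacement rule contradicts 8.2, and its 35 cannot be met under the cap unless nobody is lost.

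Three stronger readings are not supported:
- That the trial's significance claim is in doubt. At the effect size the plan expects, power is ample with any of the candidate sets.
- That the 28 in 10.2 confirms a completer analysis. It means complete data across all sessions, a different condition from finishing five days of stimulation.
- That the whole 20% loss measures the selection. Only the stopping of stimulation (2 of 32 before) comes from the restriction. Missed FU2 visits are a separate source of bias, possibly a larger one, but the documents do not give the number lost at the two-week visit alone, so it is not quantified here.

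**What to change.** 1. In 10.3, define the treated set as everyone who received any stimulation, which is already the feasibility denominator in 10.4.3. In 10.4.2, run the paired t-test on every member with HDRS-17 scores at D1 and FU2, whether or not stimulation was completed, and report stimulation completers as supportive. Amend the Feasibility clause in section 4 to match.
2. Add one sensitivity analysis for treated participants without an FU2 score, for example assuming no change from D1, noting that single imputation can understate variance. This supplies the method that 8.3 refers to. Report response and remission over all treated, stating how people without a score are counted.
3. Reconcile 10.3 with 8.2 on replacement. Replace the 35 in 10.3 with three separate numbers: treated (at most 35), expected with D1 and FU2 scores, and expected with complete data (28, as in 10.2). The second number need not equal 28, because it includes stoppers who attend FU2 and people who attend FU2 but miss later visits.
4. Reconcile 3.3.1, 6.5, 9.2.1 and 9.2.2 with 8.1, only on whether outcome data are still collected after stimulation stops.

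The cost is wording and slightly more analysis. No visit is added, since FU2 is already offered to people who stop; how many would attend is unknown. The estimate may be slightly less favourable.

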Research personnel will be easily available for the participants to contact via email or phone. The inclusion criteria state that each participant must be able to understand all risks and benefits associated with this study. We will be asking each participant to answer questions about the consent form to determine that the study process and the duration of participation are completely understood by all participants. We will aim to have a specific research team member assigned to complete all sessions with the same participant. However, we will not require the same researcher to be present during stimulation sessions 2 through 4. The study team will work hard at forming rapport with the participant so they feel comfortable and willing to discuss what may be sensitive information. Retention will be quantified by the fraction of participants coming to each scheduled session (the data from each session will be scored and documented the day of the session).

As this study requires several days of participation in a row, we will allow participants to miss one stimulation session, if it is made up at the end of the stimulation week. If two consecutive stimulation sessions are missed, the participant will be withdrawn from participation. This schedule would permit the participant to still receive the full intervention (5 days of stimulation) without being withdrawn from the study due to unforeseen circumstances (e.g., inclement weather, car trouble).

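### The primary outcome is limited to people who complete stimulation, although the plan seeks FU2 scores from those who stop

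*Combined protocol and SAP*

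**What the plan says.** **Who is analysed.** In the objectives table (Section 4), the justification for the exploratory feasibility endpoint begins "Since the primary outcome is determined from the subgroup of people who have completed stimulation". It goes on to say that looking at the completion fraction "is important to minimize bias in case of people discontinuing study participation due to lack of perceived efficacy or symptoms worsening". The primary endpoint row has no such restriction. Section 10.3 defines no analysis set, and 10.4.2 gives only a two-sided paired t-test at alpha 0.05.

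**What is collected after stopping.** Section 8.1 says "Discontinuation from the week of stimulation does not mean discontinuation from the study", and that after withdrawal from the intervention "the participant will be contacted and invited for the FU1 survey questionnaires and for the FU2 follow-up assessment including all respective questionnaires". The schedule of activities places the HDRS-17 at FU2. The triggers in 8.1 include "A participant develops significantly increased suicidal risk", "A participant has an ASRM score greater than or equal to 6" and "The participant misses a single day of stimulation and is unable to make it up at the end of the stimulation week".

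**Where participation itself ends.** Section 6.5 says "If two consecutive stimulation sessions are missed, the participant will be withdrawn from participation". Section 3.3.1 asks a participant whose suicide risk rises to stop the study, while 9.2.1 leaves that decision to clinicians after an acute assessment. Section 9.2.1 also ends participation on hospitalisation, and 9.2.2 ends it for mania in the stimulation week.

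**Replacement.** Section 8.2 does not replace partly treated participants and caps consent at 35. Section 10.3 says that people who do not finish the intervention are replaced, and expects 35 analysable participants.

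**The concern.** In a single-arm trial the mean change in HDRS-17 from D1 to FU2 is the main result. Section 5.2 justifies the study by the lack of data on effect size, so this estimate is likely to feed the design of later trials.

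As written, an FU2 score obtained under 8.1 from someone who stopped would be collected and then left out of that mean. Section 4 sees the risk, but its remedy is descriptive: a completion fraction says how many people stopped, not how they fared. If those who stop tend to be those who do badly, the completer mean is too favourable, and nothing in the planned analysis would show by how much.

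**Working it through.** **The plan's own figures (10.2).** Exact power of the paired t-test from the noncentral t, two-sided alpha 0.05:
- dz 1.58 at 95% power: N = 8 (power 0.967; N = 7 gives 0.933).
- dz 0.55 at 80% power: N = 28 (power 0.801).
- 28 / 0.80 = 35 to consent.

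All reproduce, so the issue is the analysis set and not the sample-size arithmetic.

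**How many might stop.** In the earlier trial (10.2), 32 enrolled and 30 finished the 5-day course, so 2/32 = 6.25% did not.
- Scaled: 35 × 0.0625 = 2.2, about 2 of 35.
- Exact (Clopper-Pearson) 95% CI for 2/32: 0.8% to 20.8%; 35 × 0.0077 = 0.3 and 35 × 0.208 = 7.3, so about 0 to 7 of 35.
- The two may not both have been stimulated, and that trial used different stimulation, so the rate is only a guide.

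**Effect on the estimate.** Take 28 completers with mean change 1.58 and SD 1 (the 10.2 effect size), and add k stoppers, all with FU2 scores. If no stopper changes at all (an assumption):
- all-treated mean = 28 × 1.58 / (28 + k);
- excess of the completer mean = (28 + k)/28 − 1 = k/28;
- SD² = [27 + 28k × 1.58² / (28 + k)] / (27 + k), and t = mean × √(28 + k) / SD.

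| k | N | All-treated mean (SD units) | Completer mean too high by | t |
|---|---|---|---|---|
| 0 | 28 | 1.58 | 0% | 8.36 |
| 1 | 29 | 44.24/29 = 1.526 | 1/28 = 3.6% | 8.02 |
| 2 | 30 | 44.24/30 = 1.475 | 2/28 = 7.1% | 7.73 |
| 7 | 35 | 44.24/35 = 1.264 | 7/28 = 25% | 6.81 |

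No change is not the worst case. If stoppers worsen by 0.5 SD, the means are (44.24 − 0.5)/29 = 1.508, (44.24 − 1)/30 = 1.441 and (44.24 − 3.5)/35 = 1.164. The excess is then 5%, 10% and 36%. If stopping is unrelated to outcome, the expected excess is zero.

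**Effect on the test.** At dz 1.58 every t above is far beyond the critical value. At dz 0.55, the smallest effect the plan targets, two unchanged stoppers move t only from 2.91 to 2.88 (p = 0.007 for both). With 7 stoppers whose mean change is zero (SD 1), power is 0.70 at N = 35, against 0.80 for 28 completers alone. The statement that the test is unaffected is therefore limited to effects near the expected one.

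**Replacement and the cap.** If everyone consented is treated, one person who stops part-way leaves at most 35 − 1 = 34 completers under the cap in 8.2. The 35 analysable participants in 10.3 and the cap in 8.2 then cannot both hold for a completer set.

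**The case against.** The best counter-argument is that the restriction rests on a subordinate clause in the justification of an exploratory endpoint. The primary endpoint row and 10.4.2 do not repeat it, and 8.1 collects FU2 from stoppers for research. On that view the analysis set is merely undefined. The placement is indeed odd, but the clause is the only explicit statement on the matter and nothing contradicts it. An analyst following the plan would exclude stoppers. Either reading calls for a definition in Section 10.

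It can also be said that change among people who received the full course is a legitimate pilot question, openly disclosed, and that the shift is small against the uncertainty. With N = 28 and SD 1 the 95% CI half-width is 2.05/√28 = 0.39 SD, while two unchanged stoppers shift the mean by 1.58 − 1.475 = 0.105 SD, about a quarter of that. This stands as a limit on severity. It does not justify leaving out scores already collected, and with 7 stoppers the shift is 1.58 − 1.264 = 0.316 SD, about 0.8 of the half-width.

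Three stronger readings are tempting, and the documents do not support them:
- A reader might take the 28 completers in 10.2 as confirming the restriction. There the number refers to a complete dataset, derived from people who finished all study sessions including follow-up.
- A reader might infer that FU2 will not be obtained from people who deteriorate. Section 8.1, the dedicated section, seeks it. The conflicting wording in 3.3.1 and 9.2.1 is partly subject to clinical decision, and 9.2.2 may apply only to confirmed mania. Sessions missed because of weather or transport, the kind of cause 6.5 mentions, would not be expected to bias the mean.
- A reader might treat 2 of 35 as the most that could stop. It is a scaled point estimate; the interval reaches about 7.

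**Conclusion.** The concern holds. The plan's only explicit rule limits the primary outcome to stimulation completers, leaves out FU2 scores that 8.1 sets out to collect, and offers a completion fraction that cannot correct the mean. Sections 10.3 and 8.2 also contradict each other on replacement. The wording on ending participation in 6.5, 3.3.1, 9.2.1 and 9.2.2 is a secondary matter: it might cost some of the scores needed.

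The bias is probably small, but the documents cannot fix its size. It is zero if stopping is unrelated to outcome. If stoppers do not change, the completer mean is about 4%, 7% or 25% too high with 1, 2 or 7 stoppers. These figures assume 28 completers, dz 1.58 and FU2 scores for all stoppers. A reader might infer that a significant result could be an artefact of the completer rule. At dz 1.58 that is not supported: t stays at 6.8 or more in the table. The size of the reported improvement is what is at risk. This should be corrected, but it does not undermine the trial.

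**What to change.** 1. Amend Section 4, 10.3 and 10.4.2 so that the primary paired analysis includes every participant who received any stimulation and has D1 and FU2 HDRS-17 scores. Keep the completer analysis as a sensitivity analysis. Report how many treated participants lack FU2. Section 10.4.3 already uses any stimulation received as its denominator.
2. Correct 10.3 to agree with 8.2: partly treated participants are not replaced. Revise the expectation of 35 analysable participants accordingly.
3. Secondary: state that 8.1 governs FU2 collection once stimulation stops, subject to consent and clinical judgement, and refer to it from 6.5, 3.3.1, 9.2.1 and 9.2.2. The rules for stopping stimulation stay as they are.

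The cost is wording, plus at most a few FU2 visits that 8.1 already foresees. The estimated improvement may be slightly smaller, and the headline result will no longer describe completers alone.

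The set is still complete-case, so this does not address people who finish stimulation but miss FU2. That loss may be larger: in the earlier trial 30 finished stimulation and 26 attended both follow-ups, so at least 30 − 26 = 4 of the 30 lacked at least one. How many missed the 2-week visit is not given. Section 8.3 says the analysis plan allows for missing data, but Section 10 gives no method, so that needs its own provision.
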